5.0 TIME AND EVENTS TABLE

The baseline survey will take place after the participant's consent. The post-PERC survey will be about 16 weeks post baseline depending on the participant's schedule.

5.1 Time and Events Table

	Baseline (T1) PERC & Control	PERC Intervention	4, 8, and 12 months post- baseline (T2, T3, and T4) PERC & Control
Screening	X		
Informed Consent	X		
Randomization	X		
Quality of Life: Functional Assessment of Cancer Treatment (FACT-G): ^{176, 17*}	X	Phone and/or Zoom contact, with Questionnaires at time points	X
Personal factors: Demographics (age, race/ethnicity, income, and education)	X		
Charlson Comorbidity Index_Brief ^{177,178A}	X		X
PROMIS measures of pain, ¹⁷⁹ fatigue, ¹⁸⁰ sleep disturbance ^{181,182}	X		X
PROMIS Cancer Anxiety and Depression measures ^{182,185}	X		X

Couple factors: Relationship quality: Dyadic Adjustment Scale—Brief ^{186-188*}	X		X
Holmes and Rahe Scale	X		X
Cancer-related factors: Type of treatment [#]	X		X
Prostate cancer symptoms: Prostate cancer Index Composite (EPIC) ^{9,189**#}	X		X
Cancer care Financial Toxicity: COST-FACIT	x		x
Appraisal of illness: Appraisal of Illness scales ^{190,191*}	X		X
Coping Resources: Lewis Cancer Self-Efficacy Scale ¹⁹²	X		X
PROMIS Informational, Emotional, instrumental ¹⁹³⁻¹⁹⁵ and social Support ¹⁹⁶	X		X
Adapted Med Diet Screening and physical activity ^{201,202*}	X		X
Measure of Adult Sedentary Time (MOST)	X		X
eHealth Literacy Scale (eHEALS)	X		X
Modified RESIDE Physical Activity Screener	X		X
Perceived Ease of Use and Program Satisfaction ^{203,204*}			
Physical activity logs (health diary)	X		X
PERC web activity (automatic tracking)			X

6.0 UNANTICIPATED PROBLEMS

6.1 Definition

As defined by UNC's IRB, unanticipated problems involving risks to study subjects or others (UPIRSO) refers to any incident, experience, or outcome that:

- Is unexpected (in terms of nature, severity, or frequency) given (a) the research procedures that are described in the protocol-related documents, such as the IRB-approved research protocol and informed consent document; and (b) the characteristics of the subject population being studied;
- Is related or possibly related to a subject's participation in the research; and
- Suggests that the research places subjects or others at a greater risk of harm (including physical, psychological, economic, or social harm) related to the research than was previously known or recognized.

We anticipate minimum risk of this study. The PERC and NCI websites provide a series of state-of-science resources that the participants can use at their convenience. We will also refer them to their treating doctors and nurse practitioners should any serious event happen.

6.2 Reporting

We will report to the UNC IRB using the IRB's web-based reporting system any unanticipated problem that occurs during the conduct of this study and that meets **at least** the first two criteria listed in 6.1.

7.0 STATISTICAL CONSIDERATIONS

7.1 Study Design

This study is a two-arm, parallel group randomized controlled trial (RCT) to test the efficacy of PERC, a theory-based, couple-focused, tailored mHealth program aimed to improve the QOL of patients with prostate cancer and their partners. After baseline measures (T1, following consent), 250 patient-partner dyads will be randomly assigned to PERC or to control (usual care plus the NCI website) groups. Participants will complete three surveys to assess the short, intermediate, and long-term effects of PERC: at 4 months post-T1 (T2), 8 months post-T1 (T3), and 12 months post-T1 (T4).

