1.0 BACKGROUND AND RATIONALE

1.1 Study Synopsis

In this study, we propose to test the efficacy of a couple-focused, web-based tailored prostate cancer symptom management program (PERC) in a randomized clinical trial. We will use a two-group (**PERC versus NCI website**) randomized controlled design and collect data at baseline (T1) and 4 (T2), 8 (T3), and 12 months (T4) among 800 patients (400 patient – partner dyads) completing initial treatment for localized prostate cancer and their intimate partners.

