2.0 STUDY OBJECTIVES/AIMS AND ENDPOINTS

In this randomized controlled trial, we will examine the efficacy of a couple-focused, web-based tailored prostate cancer symptom management program (PERC). We will use a two-group (**PERC versus NCI website**) randomized controlled design and collect data at baseline (T1) and 4 (T2), 8 (T3), and 12 months (T4) among 800 patients (400 patient - partner dyads) completing initial treatment for localized prostate cancer and their intimate partners.

2.1 Primary Objective: Assess the efficacy of PERC for improving QOL (total score and subscale scores of the physical, social, mental, and functional domains) among patients and their intimate partners.

H 1: Patients and their intimate partners randomized to PERC will report a larger increase in QOL scores (as assessed by the Functional Assessment of Cancer Treatment, FACT-G) than those randomized to the control group (usual care plus the National Cancer Institute prostate cancer website, the NCI website) at 4, 8, and 12 months post-baseline

2.1.1 Our primary outcome is the total QOL score, and each of the QOL subdomains are secondary outcomes.

2.2 Secondary Objectives: Test the effects of PERC on symptom appraisals and coping resources.

H 2: Patients and their intimate partners randomized to PERC will report greater improvement in secondary outcomes, positive appraisals of illness and coping resources, i.e., self-efficacy in symptom management, greater social support, and use of more healthy behaviors, at follow-ups than those randomized to the control group.

2.3 Exploratory Objective: Explore whether patients' race/ethnicity, education, type of cancer treatment, and couples' relationship quality at baseline moderate the effects of PERC on patient and partner QOL at follow-ups.

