4.3 Study Details

We plan to recruit 400 patient-partner dyads(800 participants) with diverse backgrounds through the NC Central Cancer Registry rapid case ascertainment (NC CCR RCA). The RCA uses an accelerated process to capture new cases within a week of diagnosis. After receiving a report of localized prostate cancer patients from RCA, we will contact patients' physicians by letter, giving them three weeks to request that a patient not be approached for study inclusion. In one of our studies that RCA facilitated, physicians opted out 81 out of 3400 patients (2.4%) due to patients' severe mental and physical illnesses or insufficient English proficiency. ¹⁰⁸

Study participation data will be provided back to the NC Central Cancer Registry rapid case ascertainment (NC CCR RCA) every six months.

After the 3 week window, we will mail study introduction, a brochure, an opt out letter and informed consent information to potential participants. Then we will call within two weeks to assess interest in participating, answer questions, and screen for eligibility. We will use the same procedure to screen partners' eligibility after eligible patients give permission for us to contact their partner. We will obtain informed consent from eligible patients and partners *via* telephone.

After consented patients and partners independently complete the baseline survey via telephone, dyads will be randomized to PERC or the control group using a 1:1 ratio. v will generate allocation sequences by computerized randomization with randomly permuted blocks of random sizes. The Co-I statistician ([name]) will generate allocation sequences by computerized randomization with randomly permuted blocks of random sizes. *Randomization will be stratified by type of treatment*, surgery or radiation with or without hormonal therapy. Randomization will be centrally allocated using REDCap to ensure the security of randomization lists from all study personnel. After randomization, dyads will be informed of group assignment via email, mailer and/or telephone (the communication

methods participants prefer) and study activities and invited to start either the PERC or NCI program.

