7.2 Sample Size and Power

We calculated power for comparing our primary outcome (overall QOL) in the Primary Objective using a standard approach for linear mixed models. Because we will assess outcomes for patients and partners separately, we applied a Bonferroni-corrected, two-sided alpha of 0.025 to allow for separate overall tests for patients and partners. This is because, although dyadic data will be modeled simultaneously, conclusions may differ for patients and partners. Based on our pilot test of PERC, we assumed a common standard deviation for the overall QOL scores of 15 points and a within-person correlation between repeated measurements of 0.75. Also, we allowed for losing up to 7% of participants every 4 months, for a total attrition of 20% through 12 months.

Under these assumptions (based on our preliminary studies), we report power for two scenarios, first allowing for attenuating effects, and then assuming constant effects. For the first scenario, we assumed that, on average, PERC would result in improved QOL relative to the control condition, but that these benefits might realistically be expected to decrease somewhat over time. Assuming that the mean difference between groups would be 7.5 points in overall QOL scores at 4 months (i.e., a moderate effect size of 0.5 that would represent a clinically meaningful difference immediately following the intervention) and that this would decrease by 15% every 4 months, randomizing 125 dyads per group would provide 90% power to reject the overall null hypothesis of no differences between groups across all time points. Furthermore, with this scenario, this sample size would provide 94% power for the 4-month comparison, 83% power for the 8-month comparison, and 51% power for the 12-month comparison. For the second scenario, we assumed that the intervention has a constant effect of 6.5 points at each time point (an effect size of 0.43). This sample size will provide at least 80% power for each comparison.

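### The protocol sets the trial at 400 dyads in three sections but randomises and powers 250 in the statistical section, and gives no power for 400.

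*Combined protocol and SAP*

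**What the plan says.** Three sections give 400 dyads. Section 1.1 describes the two-group randomised design with surveys at "4 (T2), 8 (T3), and 12 months (T4) among 800 patients (400 patient – partner dyads) completing initial treatment". Section 2.0 repeats this: "among 800 patients (400 patient - partner dyads) completing initial treatment for localized prostate cancer". Section 4.3 adds: "We plan to recruit 400 patient-partner dyads(800 participants) with diverse backgrounds". The 800 counts both members of each dyad.

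Two sections give 250. Section 7.1 states: "250 patient-partner dyads will be randomly assigned to PERC or to control". Section 7.2 reports that "randomizing 125 dyads per group would provide 90% power to reject the overall null hypothesis", then 94% power at 4 months, followed by "83% power for the 8-month comparison, and 51% power for the 12-month comparison". Its second scenario, a constant 6.5 points, refers to the same sample size and claims at least 80% power for each comparison.

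On losses, section 7.2 says: "we allowed for losing up to 7% of participants every 4 months, for a total attrition of 20% through 12 months". Section 4.3 randomises dyads 1:1 once both members have completed the baseline survey, and mentions no loss between recruitment and randomisation.

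**The concern.** The number randomised decides when enrolment ends. Stopping at 250 departs from sections 1.1, 2.0 and 4.3, while continuing to 400 departs from section 7.1. Section 8.4 requires the study to be run exactly as the approved protocol describes, which cannot be done with two targets. Section 7.4.2 says there is no DSMB, and no other rule for ending enrolment is given. Any stopping point between 250 and 400 could therefore be defended from the text after the fact.

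If 400 is meant, up to 150 dyads (300 people) would be enrolled with no sample-size argument behind them. If 250 is meant, three sections overstate the size of the trial.

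**Working it through.** **1. The gap.** 400 − 250 = 150 dyads, or 300 people. That is 150/250 = 60% of the smaller number and 150/400 = 37.5% of the larger.

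**2. Can the stated attrition bridge it?** Losing 7% every 4 months leaves 0.93³ = 0.804 at 12 months. Then 400 × 0.804 = 321.7 and 250 × 0.804 = 201.1. Neither links 400 to 250. The 125 per group is also already the number randomised, before losses.

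**3. Could 400 be recruited and 250 randomised?** This needs a loss of 1 − 250/400 = 37.5% before randomisation. None is stated, and sections 1.1 and 2.0 attach follow-up to 12 months to the 400.

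**4. Which number does section 7.2 belong to?**

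Inputs from section 7.2: SD 15, within-person correlation 0.75, two-sided alpha 0.025, retention 0.93, 0.93² and 0.93³. Scenario 1 starts at 7.5 points and falls 15% every 4 months. Scenario 2 is 6.5 points throughout. The overall test is the 3-degree-of-freedom contrast in section 7.3.

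Assumptions made here: compound symmetry, monotone dropout, no baseline adjustment.

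Method: for each arm, the information matrix for the three follow-up means is summed over dropout patterns. The covariance V of the group differences is twice its inverse.

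- Each time point: power = Φ(δ/SE − 2.241). The opposite tail is negligible.
- Overall: noncentral chi-square on 3 df with λ = δ′V⁻¹δ and critical value 9.348.

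Scenario 1 at 125 per group, with the decay as written (7.5, 7.5 × 0.85 = 6.375, 7.5 × 0.85² = 5.419):

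- 4 months: SE = √(2 × 225/(125 × 0.93)) = 1.967. 7.5/1.967 − 2.241 = 1.571, giving 94.2% (stated 94%).
- 8 months: SE = 2.000. 6.375/2.000 − 2.241 = 0.946, giving 82.8% (stated 83%).
- 12 months: SE = 2.027. 5.419/2.027 − 2.241 = 0.432, giving 66.7% (stated 51%).
- Overall: λ = 15.01, giving 86.7% (stated 90%); an F reference gives 85.7%.

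The first two figures reproduce and the last two do not. A third decay step at 12 months, 7.5 × 0.85³ = 4.606 points, gives 51.2% at 12 months and 89.0% overall (88.2% by F), close to the stated values. That step is an inference and is not in the text.

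| Effects (points) | Dyads per group | Overall | 4 mo | 8 mo | 12 mo |
|---|---|---|---|---|---|
| 7.5, 6.375, 5.419 | 125 | 86.7% | 94.2% | 82.8% | 66.7% |
| 7.5, 6.375, 5.419 | 200 | 98.2% | 99.5% | 96.3% | 87.3% |
| 7.5, 6.375, 4.606 | 125 | 89.0% | 94.2% | 82.8% | 51.2% |
| 7.5, 6.375, 4.606 | 200 | 98.8% | 99.5% | 96.3% | 73.6% |
| 6.5 throughout | 125 | 80.0% | 85.6% | 84.4% | 83.3% |
| 6.5 throughout | 200 | 96.0% | 97.4% | 96.9% | 96.5% |

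No scenario 1 figure in section 7.2 matches 200 per group. The claim of at least 80% for each comparison in scenario 2 is met at 125.

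**5. Does 400 follow from the inputs?** Under this unadjusted model, 90% overall power in scenario 1 needs 137 per group (274 dyads) with the decay as written, or 129 per group (258 dyads) with 4.606 points. Neither is 400.

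**The case against.** The strongest reply concerns severity. Section 7.2 justifies 125 per group, and 200 per group has more power under the same inputs, so the stated power is a floor. The endpoint, alpha, test and analysis set do not depend on the number randomised, and no interim analysis is described. The protocol calls the study minimal risk, and control dyads keep usual care. All of this is true, and it rules out a power shortfall. It does not supply a target, and without one nothing fixes when enrolment ends.

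A second objection is that 137 or 129 per group is not what the planned analysis needs. Section 7.3 adjusts for the baseline score. If the 0.75 correlation also applies to baseline, the overall power at 125 per group exceeds 99%, and about 50 per group reaches 90%. This stands: the figures in step 5 show only that the inputs do not lead to 400, and they are no reason to think 250 too few. The match at 94% and 83% indicates that the plan's own calculation was unadjusted.

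Third, the schema in section 4.1 is not visible in the copy reviewed, and a flow diagram might show recruited and randomised counts. The statement that nothing reconciles the numbers is therefore limited to the readable text. Even so, sections 1.1 and 2.0 tie data from T1 to T4 to 400 dyads, which a recruited-versus-randomised split would contradict.

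Finally, the 12-month decay is a separate matter from the 400/250 conflict. It is kept here only because the power paragraph has to be revisited anyway.

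**Conclusion.** The inconsistency holds and must be corrected. Sections 1.1, 2.0 and 4.3 set 400 dyads, sections 7.1 and 7.2 set 250, and neither the stated attrition nor any stated loss before randomisation connects them. This conclusion rests on the text alone and needs no modelling assumption. The ambiguity covers 150 dyads (300 people).

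The recalculation adds that section 7.2 was computed for 250 and that power for 400 is nowhere given. It rests on compound symmetry and no baseline adjustment. A secondary finding, under the same assumptions, is that the stated 51% at 12 months and 90% overall do not follow from a 15% fall every 4 months, which gives 66.7% and 86.7%.

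**What to change.** - The sponsor should confirm one number of randomised dyads, state it in sections 1.1, 2.0, 4.3, 7.1 and 7.2, and say that enrolment ends at that number.
- If 400 is current, change sections 7.1 and 7.2 to 200 per group and recompute every power figure.
- If 250 is current, correct sections 1.1, 2.0 and 4.3. If more dyads are to be recruited than randomised, give both numbers and the expected loss between them, and attach the follow-up data to the randomised number.
- In either case, state in section 7.2 which 12-month effect was used in scenario 1 and whether the calculation adjusts for baseline, so that the text and the power figures agree.

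The cost is protocol wording and a recomputed power paragraph. No participants are needed beyond the target the sponsor confirms.

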7.2 Sample Size and Power

We calculated power for comparing our primary outcome (overall QOL) in the Primary Objective using a standard approach for linear mixed models. Because we will assess outcomes for patients and partners separately, we applied a Bonferroni-corrected, two-sided alpha of 0.025 to allow for separate overall tests for patients and partners. This is because, although dyadic data will be modeled simultaneously, conclusions may differ for patients and partners. Based on our pilot test of PERC, we assumed a common standard deviation for the overall QOL scores of 15 points and a within-person correlation between repeated measurements of 0.75. Also, we allowed for losing up to 7% of participants every 4 months, for a total attrition of 20% through 12 months.

Under these assumptions (based on our preliminary studies), we report power for two scenarios, first allowing for attenuating effects, and then assuming constant effects. For the first scenario, we assumed that, on average, PERC would result in improved QOL relative to the control condition, but that these benefits might realistically be expected to decrease somewhat over time. Assuming that the mean difference between groups would be 7.5 points in overall QOL scores at 4 months (i.e., a moderate effect size of 0.5 that would represent a clinically meaningful difference immediately following the intervention) and that this would decrease by 15% every 4 months, randomizing 125 dyads per group would provide 90% power to reject the overall null hypothesis of no differences between groups across all time points. Furthermore, with this scenario, this sample size would provide 94% power for the 4-month comparison, 83% power for the 8-month comparison, and 51% power for the 12-month comparison. For the second scenario, we assumed that the intervention has a constant effect of 6.5 points at each time point (an effect size of 0.43). This sample size will provide at least 80% power for each comparison.

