7.3 Data Analysis Plans

A detailed analysis plan will be developed prior to initiating the study; the following is a summary of the proposed plan. Unless otherwise specified, all analyses will include all randomized participants, in the arm to which they are randomized, regardless of the extent of intervention received (intention-to-treat).

Primary Objective: We will compare the longitudinal mean change in overall QOL between groups using analysis of covariance (ANCOVA), conducted using linear mixed models. Data for patients and partners will be fit together in the same model (accounting for within-dyad correlation), which will allow us to readily assess for differential treatment effects between patients and partners. Mixed models will allow for the inclusion of all observed data for all dyads, assuming any missing data are

missing at random. Each model will include fixed effects (separate for patient or partner) for group, month, group-by-month interactions, the baseline value of the outcome scale, baseline treatment type (surgery and radiation +/-hormonal therapy), number of baseline comorbidities, baseline couple relationship quality, baseline family disruptions, age, race/ethnicity, education, income, and number of people supported by the income. These covariates were selected because they are potentially associated with QOL. Models will include random dyad and participant nested within dyad effects to account for within-dyad and within-person correlations between longitudinal responses. For the primary comparison, separately for each participant type, we will first test for any differences between groups across all 3 time points using an appropriately specified 3 degree of freedom linear contrast. Only if this test is significant ($p \leq 0.025$), will we test for group differences at each time point.

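### Holm could replace the fixed Bonferroni 0.025 for the patient and partner overall tests: same 5% for those two tests, no rejection lost, but a gain worth having only if effects are smaller than planned

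*Combined protocol and SAP*

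**What the plan says.** Section 7.2 sets the significance level for the primary outcome, total QOL: "we applied a Bonferroni-corrected, two-sided alpha of 0.025 to allow for separate overall tests for patients and partners". Its reason is that conclusions may differ between the two roles. The power statement follows at that level: "randomizing 125 dyads per group would provide 90% power to reject the overall null hypothesis of no differences between groups across all time points".

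Section 7.3 carries the rule into the analysis. The plan says that "separately for each participant type, we will first test for any differences between groups across all 3 time points". This overall test is a joint contrast with 3 degrees of freedom, one for each follow-up month. The gate to the individual months is fixed: "Only if this test is significant ($p \leq 0.025$), will we test for group differences at each time point".

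Neither section mentions a step-down rule or the passing of alpha from one role to the other. A 5% family-wise rate is not stated in words; it follows from 2 × 0.025. The level of the time-point tests is not stated either. Section 7.3 describes itself as a summary, with a detailed analysis plan to follow.

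**The concern.** The split of alpha exists to cover two overall tests. Under fixed Bonferroni each role must reach 0.025 whatever the other role shows. Holm relaxes the second threshold to 0.05 once the first test has succeeded. It does so without exceeding 5% for the pair and without any assumption about the correlation within couples.

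H1 in section 2.1 claims benefit for patients and for their partners. A result in both roles is therefore a natural target, and it is the quantity that a fixed split reduces most. What is at stake is some power for the second role, not the validity of the trial.

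**Working it through.** **Inputs.** Section 7.2: "we assumed a common standard deviation for the overall QOL scores of 15 points"; "a within-person correlation between repeated measurements of 0.75"; 7% loss every 4 months, so 93%, 86.5% and 80.4% retained; 125 dyads per group; two-sided 0.025. Section 4.3: 1:1 allocation. Effects from 7.2: 7.5 points at 4 months falling by 15% every 4 months, or a constant 6.5 points. The patient-partner correlation is not given; 0 to 0.6 is assumed.

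**Method.** Overall power is that of a 3-df chi-square test with noncentrality λ = d′V⁻¹d, where d holds the three group differences and V is their covariance under monotone dropout.

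**1. The plan's own figures.**
- Alpha: 0.05 / 2 = 0.025, exact.
- Follow-up scores with no baseline adjustment and a 12-month effect of 7.5 × 0.85³ = 4.61: λ = 15.96, overall power 89.0%, and 94.2%, 82.8% and 51.2% at 4, 8 and 12 months. The plan states 90%, 94%, 83% and 51%.
- The literal 12-month effect, 7.5 × 0.85² = 5.42, gives λ = 15.01, overall power 86.7% and 66.7% at 12 months. This does not match the stated 90% and 51%; it is a separate point to reconcile.
- The stated powers are thus consistent with an analysis that does not use the baseline score, and with time-point tests at 0.025.

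**2. Holm against Bonferroni.** Let a be power at 0.025 and b power at 0.05 for one role, with equal effects and independent roles.
- Per role: Bonferroni a; Holm a + (b − a)a.
- Both roles: Bonferroni a²; Holm a² + 2(b − a)a.
- At least one role: identical, because both rules compare the smaller p-value with 0.025.

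**3. Without baseline adjustment, 125 per arm.**

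| Effect | Per role | Both roles |
|---|---|---|
| Fading, literal | 86.7% → 91.1% | 75% → 84% |
| Constant 6.5 | 80.0% → 85.4% | 64% → 75% |

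In 1,000,000 simulated trials per setting, with correlation 0 to 0.6 and the effects that reproduce the plan's powers, per-role power went from 89.0% to 92.1–92.9% and both roles from 79.4–82.3% to 87.1–88.4%. In no simulated trial did Bonferroni reject where Holm did not.

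**4. With the baseline score as covariate, as 7.3 specifies.** The residual variance is 225 × (1 − 0.75²) = 98.44 and the covariance 225 × (0.75 − 0.75²) = 42.19.
- Fading, literal: λ = 41.02, a = 99.98%; Holm 99.99%.
- Constant 6.5: λ = 38.88, a = 99.97%; Holm 99.99%.
- Constant 4 points (assumption): λ = 14.72, a = 85.89%, b = 91.16%. Per role 0.8589 + 0.0527 × 0.8589 = 90.4%. Both roles 0.8589² = 74% → 0.7377 + 2 × 0.0527 × 0.8589 = 83%.
- Constant 4 points with 200 per arm (the 400 dyads of sections 1.1, 2.0 and 4.3): per role 98.0% → 99.0%, both 96% → 98%.

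**5. Error for the two overall tests.** Both nulls true: 4.6–5.0% under either rule. Patient effect present, partner effect zero (unadjusted, correlation 0 to 0.6): partner false-positive rate 2.5% under Bonferroni and 4.7–4.8% under Holm. It approaches 5% as patient power approaches 100%. Patient power moves only from 89.0% to 89.1%.

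**6. Error including time-point claims.** Assume each time-point test at 0.025 behind its gate, independent roles, a true 7.5-point effect at 4 months only, and 125 per arm.
- Patients affected, partners not: the chance of any false overall or time-point claim is 6.6% (unadjusted) to 7.1% (adjusted) now, and 9.0% to 9.5% under Holm.
- Both roles affected at 4 months only: about 8% to 9% now. It stays there under Holm, and also if alpha is released to the other role only after all of a role's tests are rejected.

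**The case against.** The strongest reply is that nothing is wrong. Bonferroni is valid, prespecified, consistent between 7.2 and 7.3, and justified by the wish to draw separate conclusions. That stands: this is a missed efficiency.

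A reader might infer that the trial gives up power for no error-rate benefit. The plan and its figures do not support that. When one role has no effect, a case that 7.2 allows for in saying that conclusions may differ, Bonferroni holds that role's false-positive rate at 2.5%, while Holm lets it rise to just under 5%.

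A reader might also take the unadjusted gains in step 3 as the gain for this trial. They belong to a model that omits the baseline score, whereas 7.3 includes it. Under that model the planned effects leave almost nothing to gain, and the 4-point effect that shows a visible gain is not in the documents.

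Finally, Holm protects only the two overall tests. Three time-point tests at an unadjusted level behind a 3-df gate are not controlled at 5% now, and Holm makes that somewhat worse (step 6). Holding back the release of alpha does not by itself repair it. All of this stands and limits the recommendation; none of it removes Holm's advantage for the two overall tests.

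**Conclusion.** The point holds as a cheap, optional improvement to the two overall tests. Holm meets the 5% that the plan implies for them under any dependence and loses no rejection.

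The benefit is conditional. It is negligible at the planned effects with the planned model. It is about 4 to 5 points per role and 9 points for both roles at an assumed constant 4-point effect with 125 per arm, and about 1 and 2 points with 200 per arm. It adds almost nothing if only one role benefits. These figures assume SD 15, exchangeable correlation 0.75, the stated dropout, equal effects and independent roles. In the unadjusted simulations, correlation up to 0.6 made the gains somewhat smaller.

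**What to change.** In 7.2 and 7.3, replace the fixed gate by Holm for the two overall tests: the smaller p-value at 0.025 and, if significant, the other at 0.05. Open the time-point tests for each role whose overall null is rejected. State that the 5% covers the two overall tests only and that the time-point tests are follow-up at 0.025. Name the higher false-positive rate for a role with no effect as the accepted price.

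If the sponsor wants the 5% to cover time-point claims as well, the three tests within each role also need a multiplicity correction at that role's level, and alpha should pass to the other role only after all of that role's tests are rejected. That costs power for the monthly claims and leaves less of Holm's gain.

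The change needs no extra data or participants, and power calculated at 0.025 remains conservative. It does mean rewriting the gate in 7.3 and defining a level that is now unstated. The detailed analysis plan promised in 7.3 is a natural place for it, fixed before any unblinded data are seen.

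### In section 7.2 the 90% overall power and the 51% power at 12 months do not follow from the stated fading effect; the written inputs give about 87% and 67%

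*Combined protocol and SAP*

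**What the plan says.** Section 7.2 gives these planning inputs:

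- Error rate: "we applied a Bonferroni-corrected, two-sided alpha of 0.025 to allow for separate overall tests for patients and partners".
- Variability: a common "standard deviation for the overall QOL scores of 15 points and a within-person correlation between repeated measurements of 0.75".
- Attrition: "we allowed for losing up to 7% of participants every 4 months, for a total attrition of 20% through 12 months".
- Fading scenario: "the mean difference between groups would be 7.5 points in overall QOL scores at 4 months", and "this would decrease by 15% every 4 months".

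From these it concludes that 125 dyads per group "would provide 90% power to reject the overall null hypothesis of no differences between groups across all time points", and it reports 94%, 83% and 51% for the 4-, 8- and 12-month comparisons. For a second scenario, a constant 6.5 points, it reports at least 80% for each comparison and no overall power.

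Section 7.3 defines the overall test, separately for patients and partners, as one made "using an appropriately specified 3 degree of freedom linear contrast". The visits are tested only if that test reaches p ≤ 0.025. The model adjusts for the baseline score. Section 7.2 does not state the degrees of freedom or the baseline adjustment behind its figures.

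**The concern.** The paragraph supplies enough inputs to check all four fading-scenario figures. Two of them come out as stated and two do not, so the set cannot all rest on the effects described in the text. The larger gap is at 12 months, about 16 percentage points. The smaller one, about 3 points, concerns the primary test, which also controls access to every visit-level claim.

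A reader cannot tell which long-term effect the trial was planned around: the one the text describes or the one the figures imply. The constant scenario adds a gap of a different kind. Its per-visit powers are given without the power of the test that must be passed first.

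**Working it through.** **Inputs (section 7.2).** Two-sided alpha 0.025 per participant type; SD 15; correlation 0.75, taken as equal between all visits; 125 per group; retention 0.93, 0.93² = 0.865 and 0.93³ = 0.804. Effects: 7.5, then 7.5 × 0.85 = 6.375, then 7.5 × 0.85² = 5.42. No baseline adjustment at first.

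**Covariance of the three group differences.** The within-person covariance Σ has 15² = 225 on the diagonal and 0.75 × 225 = 168.75 off it. The fractions last seen at 4, 8 and 12 months are 0.0651, 0.0605 and 0.8044 (the other 0.07 give no follow-up). Information per arm is 125 × Σₖ pₖ Σₖ⁻¹, where Σₖ covers the visits observed. V is twice its inverse. The standard errors are 1.967, 2.000 and 2.027. As a check on the first, √(2 × 225 / (125 × 0.93)) = 1.967.

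**Formulas.** Per visit: power = Φ(d/SE − 2.241). Overall: λ = d′V⁻¹d and power = P(χ²₃(λ) > 9.348).

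**Results for the fading scenario**

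| | Stated | Effects as written (12 months: 5.42) | 12-month effect 4.61 |
|---|---|---|---|
| 4 months | 94% | Φ(3.812 − 2.241) = 94.2% | 94.2% |
| 8 months | 83% | Φ(3.188 − 2.241) = 82.8% | 82.8% |
| 12 months | 51% | Φ(2.673 − 2.241) = 66.7% | Φ(2.272 − 2.241) = 51.2% |
| Overall, 3 df | 90% | λ = 15.01: 86.7% | λ = 15.96: 89.0% |

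Reading the 15% as linear (12-month effect 7.5 × 0.70 = 5.25) gives 87.0% overall and 63.6% at 12 months, so that reading does not rescue the figures. An F reference with 230 denominator df gives 85.9% overall on the written effects, and a simulation of the fitted mixed model gives 87%.

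**Working back from the 51%.** A power of 51% needs d = (2.241 + 0.025) × 2.027 ≈ 4.6 points. That is close to 7.5 × 0.85³ = 4.61, one more 15% step than the text describes.

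**Constant scenario.** Per visit: Φ(6.5/1.967 − 2.241) = 85.6%, then 84.4% and 83.3%, so the claim of at least 80% reproduces. Overall, 3 df: λ = 12.90, power 80.0%. The chance of passing both the overall test and a given visit test is about 77%, 76% and 75%.

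**With baseline adjustment.** If 0.75 also holds between baseline and each follow-up, the residual variance is 225 × (1 − 0.75²) = 98.4 and the residual covariance is 168.75 − 0.75² × 225 = 42.2. Then λ = 41.0 (fading) and 38.9 (constant), and 3-df power exceeds 99.9% in both.

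**Sample size.** At 200 per group (400 dyads), unadjusted 3-df power is 98% (fading as written) and 96% (constant).

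**The case against.** The strongest reply is that this is a gap of about 3 points in a planning approximation, and that the approximation is conservative. The analysis in section 7.3 conditions on the baseline score, so the unadjusted 87% is not the power of the test that will be run. Sections 1.1, 2.0 and 4.3 also plan 400 dyads, at which the gap disappears. All of this stands, and it rules out any claim that the study is too small. It does not make the stated figures consistent: the two that reproduce do so only in the unadjusted framework at 125 per group, and there the other two fail.

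A reader might infer that the 90% came from a 1-df test of the average difference over the three follow-ups, since that gives 90.5% on the written effects. The documents do not support this. The choice of overall test cannot explain the 51%, and with the 12-month effect that does explain it, the 3-df test (89.0%) lies closer to 90% than the 1-df average (87.7%).

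Nor do the figures justify replacing the primary test. A 3-df test ahead of visit-level tests is a legitimate choice. It is less powerful than an average contrast for a sustained effect, but it can detect a benefit confined to one visit far better.

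**Conclusion.** The point holds as an internal inconsistency in section 7.2. On the written inputs, overall power is about 87% rather than 90%, and 12-month power about 67% rather than 51%. These values assume equal correlation between visits, 7% loss compounding every 4 months, 125 dyads per group and no baseline adjustment. The first two visit figures support that framework.

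The likeliest source is a 12-month effect of about 4.6 points in the calculation where the text implies 5.42. That remains an inference.

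Two stronger conclusions are not supported. The trial is not shown to be underpowered, because baseline adjustment at a correlation of 0.75 takes the planned test above 99.9%. And the 80% in the constant scenario contradicts nothing, because the plan states no overall power there. It is a missing figure, worth supplying because the overall test gates the visit comparisons.

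**What to change.** In section 7.2, do one of the following:

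1. Keep the 15% fading as written, and restate overall power as about 87% and 12-month power as about 67%.
2. If about 4.6 points was the intended 12-month effect, state it, amend the description of the fading to match, and give overall power as 89%.

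In either case, say that the figures are for the 3-df test without baseline adjustment, or recompute them for the adjusted model and state the baseline correlation assumed. Add the overall 3-df power for the constant scenario (about 80% unadjusted at 125 per group).

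First reconcile the sample size, which is 250 dyads in section 7.1 (125 per group in 7.2) but 400 in sections 1.1, 2.0 and 4.3. Then compute every figure at the agreed number.

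The cost is a short recalculation and a few sentences. The primary test, the alpha and the testing order stay as they are.
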